7.1 Sample Size Determination

Approximately 5% of patients with PSC and chronically (>6 months) elevated ALK will spontaneously experience either a clinically significant reduction in serum ALK to less \leq 1.5 times the upper limit of normal³⁸ or a reduction of > 40% of the baseline ALK value.³⁷ In this open-label pilot study, our primary objective is to determine the proportion of patients who experience curcumin treatment success, as defined by either of these two ALK endpoints. Notably; these patients are hereinafter considered historical controls.³⁹ Therefore, if treatment success is achieved in at least 30% of curcumin treated patients, i.e. a rate that is at least 25% more than the conservative estimate in historical controls, likely based on pre-clinical data, and clinically promising, this would encourage further study of curcumin in larger, randomized clinical trials in patients with PSC.

By enrolling 15 patients with PSC in our study, an exact binomial test with a nominal two-sided significance level of $\alpha=0.05$ will have approximately 90% power to detect a 25% difference in clinically significant ALK improvement between the null hypothesis of 5% (historical control) and the alternative hypothesis of 30%. In addition, if 6 of 20 PSC patients (30%) experience treatment success, the 95% exact binomial confidence interval (CI) would be 11.9% to 54.3%, suggesting that the sample size has adequate precision to not include the null hypothesis (5%) in the CI.

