12.1	FUNDING SOURCE	21
12.2	CONFLICT OF INTEREST	21
13	REFERENCES	21

List of Abbreviations

LIST OF ABBREVIATIONS

AE	Adverse Event
ALK	Alkaline phosphatase
AST	Aspartate aminotransferase (also SGOT)
CCA	Cholangiocarcinoma
CFR	Code of Federal Regulations
CRF	Case Report Form
DSMB	Data and Safety Monitoring Board
FDA	Food and Drug Administration
GCP	Good Clinical Practice
HIPAA	Health Insurance Portability and Accountability Act
IB	Investigator's Brochure
IND	Investigational New Drug Application
IRB	Institutional Review Board
LT	Liver transplantation
PHI	Protected Health Information
PI	Principal Investigator
PSC	Primary sclerosing cholangitis
SAE	Serious Adverse Event/Serious Adverse Experience
SOP	Standard Operating Procedure
UDCA	Ursodeoxycholic acid

Study Summary

Title	An Open-Label Pilot Study Evaluating the Safety and Efficacy of Oral Curcumin in Patients with Primary Sclerosing Cholangitis
Running Title	Curcumin in Patients with Primary Sclerosing Cholangitis
Protocol Number	14-002660
Phase	Phase I/II
Methodology	Open-label
Overall Study Duration	12-18 months
Subject Participation Duration	3 months
Single or Multi-Site	Single Site (Mayo Clinic in Rochester, MN)
Objectives	Determine the safety and efficacy of curcumin and whether it should be considered for further investigation in a randomized study with a larger number of patients.
Number of Subjects	15
Diagnosis and Main Inclusion Criteria	Patients with primary sclerosing cholangitis
Study Product, Dose, Route, Regimen	One 750 mg CuraMed® softgel (EuroPharma, Inc.) by mouth twice a day. Each 750 mg CuraMed® softgel supplies 500 mg of highly bioavailable BCM-95 curcumin.
Duration of Administration	12 weeks
Reference therapy	NA/no pharmacotherapy
Statistical Methodology	Mann-Whitney U test for continuous variables, Chi-square/Fisher's exact test for categorical variables.

1 Introduction

This document is a protocol for a human research study. This study will be carried out in accordance with the applicable United States government regulations and Mayo Clinic research policies and procedures.

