3.1 General Design

We propose to conduct an open-label pilot study to preliminarily assess the efficacy and safety of oral curcumin in adult patients with PSC. Fifteen patients with PSC will receive one 750 mg CuraMed® softgel (EuroPharma, Inc.) by mouth twice a day for 12 weeks. Of note, each 750 mg CuraMed® softgel supplies 500 mg of highly bioavailable BCM-95 curcumin. A positive study, based on significant improvement in serum liver biochemistries, will establish the basis for further evaluation of curcumin in a larger, longer-term clinical trial.

Table 1 in section 6 summarizes the patient evaluation and study procedures. Briefly, prior to study entry, a complete history will be obtained and physical examination performed. Serum Alkaline Phosphatase, AST, total bilirubin, albumin, C-reactive protein, complete blood count, and creatinine will be measured. A blood pregnancy test will be performed on female patients of child bearing potential. Standardized questionnaires regarding health status (SF-36 Health Survey and Chronic Liver Disease Questionnaires), fatigue (Fisk Fatigue Impact Scale) and pruritus (5-D Pruritus scale) will be completed by participants at baseline and at 12 weeks. Phone calls will be made to participants weekly during the study, at completion of the study (i.e. at 12 weeks of therapy) and/or early termination, and at two weeks after completion of the study to monitor for any adverse events or effects of the study drug. Study staff will specifically inquire about local and systemic adverse effects including gastrointestinal upset, nausea, diarrhea, signs of anemia (e.g., weakness, fatigue), and rash; during weekly phone or in person

interviews. Participants will be instructed to contact study nurse coordinators with the development of any possible symptoms related to therapy.

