 Total bilirubin
 C-reactive protein
 Complete blood count (CBC)
 INR
 Creatinine
 Sodium
 Albumin
 Stored serum

Questionnaires
 Health status
 Pruritus
 Fatigue

Phone call to assess for AEs, concomitant medications, and study drug compliance. Note a local laboratory can be used for obtaining the blood samples if subject is unable to return to Mayo. Questionnaires can be mailed to subject if unable to return to Mayo or respond over the phone. Remaining study medication can be returned by mail to study team.

Post Treatment Assessment Week 14 (+- 7 days) (2 weeks after stopping study medication)
 Phone call to assess for AEs, concomitant medications

Table 1. Patient evaluation and study procedures

n=20 patients with PSC	Entry	3 weeks	8 weeks	12 weeks	2 weeks after study completion (i.e. 14 weeks)
Medical history and physical examination	X				
Serum laboratory tests*					
ALK	X	X		X	
AST	X	X		X	
ALT	X			X	
Total bilirubin	X	X		X	
C-reactive protein	X	X		X	
Complete blood count	X	X		X	
INR	X			X	
Creatinine	X	X		X	
Sodium	X			X	
Albumin	X	X		X	
Stored serum **	X			X	
Pregnancy test ***	X				
Questionnaires					

Health status	X			X	
Pruritus	X			X	
Fatigue	X			X	
Phone calls†		X	X	X	X

* At study entry, approximately 2 teaspoons of blood will be collected for biochemical testing. At 3 and 12 weeks, approximately 1 teaspoon will be collected for biochemical testing.

**Serum collected at baseline and at the conclusion of the study will be stored for potential future assays to explore mechanisms of action in the pathogenesis of PSC if the study drug seems beneficial.

***For female patients only.

†Will be performed for safety and compliance monitoring as described above and documented accordingly.

7 Statistical Plan

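### Sections 3.1 and 7.1 describe the result that supports going forward differently; at n=15, 4 successes reject the 5% null but miss the 30% mark

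*Combined protocol and SAP*

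**What the plan says.** The Study Summary gives the objective as determining safety and efficacy and "whether it should be considered for further investigation in a randomized study with a larger number of patients". Two sentences say what kind of result would support that step.

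- **Section 7.1** says larger randomized trials would be encouraged "if treatment success is achieved in at least 30% of curcumin treated patients". Success is the alkaline phosphatase (ALK) response.
- **Section 3.1** says: "A positive study, based on significant improvement in serum liver biochemistries, will establish the basis for further evaluation". It does not say which biochemistries, which test or what threshold.

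Section 7.1 also contains the power statement. It begins "By enrolling 15 patients with PSC in our study" and claims, for a two-sided 0.05 exact binomial test of 5% against 30%, "approximately 90% power to detect a 25% difference in clinically significant ALK improvement". It then supports the sample size with a worked interval for 6 of 20 patients, 11.9% to 54.3%, noting that this excludes 5%. The figure of 20 also survives in Table 1 of section 6 ("n=20 patients with PSC"), although the Study Summary and sections 3.1, 4.3 and 7.1 all give 15.

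Section 3.2 makes the ALK response the primary endpoint, and section 3.3 makes AST, bilirubin and albumin secondary. Sections 7.2 and 7.3 give no decision rule and do not rank these statements.

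**The concern.** The value 30% does two jobs in section 7.1. It is the assumed true rate under the alternative, and it is also an observed rate to be reached. An observed rate falls below its true value roughly half the time, so a mark set at the alternative cannot have the power quoted for the test. A reader who takes the 30% sentence as the criterion and the 90% as its power will be misled.

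The test and the mark also separate results differently. Some results are significant against 5% but fall short of 30%, and the plan does not say how to describe them.

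Section 3.1 adds a different looseness. Because its biochemistries are not tied to the primary endpoint, a significant fall in AST would satisfy its wording even if the ALK response failed. In an open-label single-arm study, the reading should be settled before results are seen.

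**Working it through.** **Inputs.** n = 15, null rate 5%, alternative 30%, two-sided exact binomial test at 0.05, and a 30% observed mark (all section 7.1); leftover n = 20 (section 7.1 interval and Table 1). The plan gives no dropout allowance, so all patients are taken as evaluable.

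**Formula.** P(X ≥ k) = Σ C(n, j) p^j (1 − p)^(n − j), summed over j = k to n. Intervals are exact (Clopper-Pearson).

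**The plan's own figures first.** For 6 of 20 the exact interval is 11.9% to 54.3%, which reproduces. The power of about 90% reproduces at n = 20: the test rejects at 4 or more of 20, with P(X ≥ 4) = 1.59% at a 5% rate and 89.3% at a 30% rate. At n = 15 the exact test gives 70.3% or 87.3%, depending on the two-sided version.

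**Results at n = 15.** The smallest whole number at or above 0.30 × 15 = 4.5 is 5, so the 30% mark needs 5 successes.

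| Successes (k) | Observed rate | P(X ≥ k) at 5% | P(X ≥ k) at 30% | Exact 95% CI | Rejects 5%? | Reaches 30%? |
|---|---|---|---|---|---|---|
| 3 | 20.0% | 3.62% | 87.3% | 4.3% to 48.1% | minimum-likelihood only (p = 0.036; doubled tail 0.072) | no |
| 4 | 26.7% | 0.55% | 70.3% | 7.8% to 55.1% | yes (doubled tail 0.011) | no |
| 5 | 33.3% | 0.06% | 48.5% | 11.8% to 61.6% | yes | yes |

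**The 30% mark as a cut-off.** At a true rate of 30% it is reached 48.5% of the time and missed 100 − 48.5 = 51.5% of the time. It is reached 64.8% of the time at a true 35% and 78.3% at a true 40%. At n = 20 it needs 6 successes; at a true 30% it is reached 58.4% of the time and missed 41.6%.

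**Where test and mark disagree, at a true rate of 30%.**

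- Equal-tail test, n = 15: exactly 4 successes. C(15, 4) × 0.30^4 × 0.70^11 = 21.9%.
- Minimum-likelihood test, n = 15: 3 or 4 successes. 0.8732 − 0.4845 = 38.9%.
- n = 20: 4 or 5 successes. 0.8929 − 0.5836 = 30.9%.

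**Direction.** Five of 15 and 6 of 20 both reject 5%, and larger counts do so more strongly. No result at or above 30% fails the test.

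**Section 3.1.** No probability can be attached to this wording, because it names no variable, test or threshold. Set beside sections 3.2 and 3.3, it neither restricts a positive result to the ALK response nor excludes the secondary markers.

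**The case against.** A reader might infer that the plan holds three competing go rules. It does not. Only the 30% sentence in 7.1 and the sentence in 3.1 are expressly tied to going forward. The exact test appears in the power statement and is a success criterion by implication only.

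A reader might also infer that 30% is a stopping threshold that rejects an effective drug half the time. The text does not say so. A rate of at least 30% would encourage further study, and no sentence says a lower rate ends development. The sentence sits in the sample size section and can fairly be read as explaining the choice of alternative. Requiring significance together with a promising observed rate is a legitimate two-part standard, and the two parts are compatible because the conflict runs one way. The figure of about half is also specific to n = 15 and owes something to rounding 4.5 up to 5.

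On 3.1, the sentence is a design summary, and 3.2 and 3.3 separate primary from secondary endpoints. Rescue by a secondary marker is permitted by loose wording; nothing shows that it is planned. Section 7.2 promises Bonferroni correction for multiple comparisons, but does not say which comparisons it covers or that the primary endpoint governs.

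These points limit the claim but leave the gap. The two sentences tied to going forward differ, the 30% mark is the only numeric criterion offered for proceeding, and nothing says how 4 of 15 should be described.

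**Conclusion.** The concern holds as a mismatch of wording with a measurable consequence. Sections 3.1 and 7.1 define a supportive result differently, and within 7.1 the 30% mark does not have the power stated beside it. If used as a cut-off, it is reached 48.5% of the time at n = 15 when the true rate is 30%. A result of 4 of 15 rejects 5% but misses 30%, with probability 21.9% at that rate.

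These figures assume that all 15 patients are evaluable. The 48.5% also assumes that the mark is applied as a cut-off; the 21.9% assumes the equal-tail test. The documents do not support saying that the plan would abandon a drug with the target effect in half of trials, because they state no no-go arm. The point should be corrected, but it does not invalidate the design.

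**What to change.** In section 7.1, state one rule: the study is positive if the exact test of the section 3.2 primary endpoint rejects 5%. Name the two-sided version and its cut-off, and give its operating characteristics:

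- at least 4 of 15 (equal-tail): type I error 0.55%, power 70.3%;
- at least 3 of 15 (minimum-likelihood): type I error 3.6%, power 87.3%.

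The first agrees with the kind of interval the plan reports. Under the second, 3 of 15 rejects 5% although its exact interval (4.3% to 48.1%) includes 5%; if that version is chosen, the plan should say so. Restate the 90% power to match the choice.

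Keep 30% as the design alternative, or label it a non-binding mark of clinical promise. In section 3.1, define a positive study by the primary endpoint in section 3.2, with the other biochemistries as supportive.

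The cost is a few sentences of wording, with no added patients or data. There are two downsides: a study can then be called positive at an observed rate below 30%, and the stated power becomes less favourable. The change should be made before outcome data are reviewed.

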4.3 Subject Recruitment, Enrollment and Screening

Patients with a diagnosis of PSC will be recruited by the study staff in the Division of Gastroenterology and Hepatology at Mayo Clinic) and enrolled in the study if satisfying the above inclusion and exclusion criteria. A total of 15 patients will be enrolled.

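### Section 7.1 argues for 15 patients with a 20-patient confidence interval, and no two-sided exact test gives the stated 90% power at n=15: it is 70% or 87%, depending on a version that is not named

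*Combined protocol and SAP*

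**What the plan says.** The enrolment target is 15 in the Study Summary, section 3.1, section 4.3 ("A total of 15 patients will be enrolled") and section 7.1. The power statement in 7.1 opens "By enrolling 15 patients with PSC in our study, an exact binomial test with a nominal two-sided significance level of" 0.05 and says that this design "will have approximately 90% power to detect a 25% difference in clinically significant ALK improvement", from a null rate of 5% to an alternative of 30%.

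The next sentence changes the denominator: "if 6 of 20 PSC patients (30%) experience treatment success, the 95% exact binomial confidence interval (CI) would be 11.9% to 54.3" per cent, "suggesting that the sample size has adequate precision to not include the null hypothesis (5%) in the CI". Table 1 in section 6 is headed "n=20 patients with PSC".

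Section 7.1 also sets a bar for going further: "if treatment success is achieved in at least 30% of curcumin treated patients", "this would encourage further study of curcumin in larger, randomized clinical trials".

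Section 7.2 names no test for the primary endpoint. The Study Summary lists only chi-square or Fisher's exact tests for categorical variables. Nothing states which two-sided exact binomial test is meant or how many successes make it significant.

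**The concern.** The precision argument is made for a sample size that the trial does not have. An observed rate of 30% cannot even occur with 15 patients, because 4/15 is 26.7% and 5/15 is 33.3%. The stated power also sits closer to a 20-patient design than to a 15-patient one.

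The sample size matters here because of discreteness. With 20 patients the common two-sided exact tests share one critical count, so leaving the version unnamed does no harm. With 15 patients they differ by one success, and that success is worth 17 points of power. A reader cannot tell from the plan whether 3 of 15 would count as a positive primary result. If the version were chosen after the data were seen, the choice could settle the primary conclusion.

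**Working it through.** **Inputs (section 7.1).** n = 15, null rate p0 = 0.05, alternative p1 = 0.30, exact binomial test, two-sided α = 0.05. The precision example is 6/20 with an exact 95% interval.

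**Formulas.**
- Tail probability: P(X ≥ r | n, p) = Σ_{k≥r} C(n,k) p^k (1−p)^(n−k).
- Equal-tail test: reject if twice the smaller tail is ≤ 0.05.
- Minimum-likelihood test: the p-value is the total null probability of all outcomes no more likely than the one observed.
- Exact (Clopper-Pearson) interval for x/n: lower limit = 2.5% point of Beta(x, n−x+1); upper limit = 97.5% point of Beta(x+1, n−x).

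**Step 1. The plan's interval.** 6/20 gives 11.9% to 54.3%. This reproduces the plan's figure, but for n=20.

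**Step 2. Power at n=20.** P(X ≥ 3 | 0.05) = 0.0755, so 3 successes are not significant under either version. P(X ≥ 4 | 0.05) = 0.0159 (doubled, 0.0318), so both versions reject at 4 or more. Power = P(X ≥ 4 | 0.30) = 0.893. The exact interval for 4/20 is 5.7% to 43.7%, which excludes 5%, so test and interval agree.

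**Step 3. Critical count at n=15.** P(X ≥ 3 | 0.05) = 0.0362.
- Equal-tail: 2 × 0.0362 = 0.0724 > 0.05, so 3 is not enough. At 4, 2 × 0.00547 = 0.0109, so it rejects at 4 or more.
- Minimum-likelihood: under the null, 0, 1 and 2 successes are each more likely than 3 (0.463, 0.366 and 0.135 against 0.031), so the lower side adds nothing. The p-value is 0.0362 and the test rejects at 3 or more.

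**Step 4. Power at n=15.**

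| Version | Rejects at | Actual error | Power at 30% | Missed at 30% | True rate for 90% power |
|---|---|---|---|---|---|
| Equal-tail | ≥ 4 of 15 | 0.55% | 70.3% | 29.7% | about 39% |
| Minimum-likelihood | ≥ 3 of 15 | 3.6% | 87.3% | 12.7% | about 32% |
| Either, n=20 | ≥ 4 of 20 | 1.6% | 89.3% | 10.7% | – |

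The two rows for n=15 differ by P(X = 3 | 0.30) = 0.8732 − 0.7031 = 0.170.

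**Step 5. Other routes to 90% at n=15.** Uncorrected normal approximations give 88.1% (two-sided) and 90.8% (one-sided). With continuity correction they give 81.6% and 85.3%; the arcsine method gives 78.3% and 86.4%. Only the uncorrected approximations come within 2 points of 90%, and the plan specifies an exact test.

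**Step 6. Exact intervals at n=15.**

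| Result | Rate | Exact 95% CI | Width (points) | Excludes 5%? |
|---|---|---|---|---|
| 3/15 | 20.0% | 4.3–48.1% | 43.8 | No |
| 4/15 | 26.7% | 7.8–55.1% | 47.3 | Yes |
| 5/15 | 33.3% | 11.8–61.6% | 49.8 | Yes |
| 6/20 (plan) | 30.0% | 11.9–54.3% | 42.4 | Yes |

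At 3/15 the interval agrees with the equal-tail test and contradicts the minimum-likelihood test.

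**Step 7. The 30% bar.** With 15 patients, at least 30% means 5 or more, and P(X ≥ 5 | 0.30) = 48.5%. With 20 it means 6 or more, and P(X ≥ 6 | 0.30) = 58.4%. Both are low mainly because the bar equals the alternative rate, so this is a separate matter from the 15/20 mismatch.

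**The case against.** The best defence is that the plan says approximately 90%. The minimum-likelihood test is a standard two-sided exact test, and its 87.3% is only 2.7 points short. On that reading the defect shrinks to an outdated example and a table header. The equal-tail test spends only 0.55% of a nominal 5%, and nothing in 7.1 selects it. The interval sentence illustrates precision; it does not say that the interval decides success. Finally, this is a single-arm pilot, and the conclusion drawn from the interval survives at both 4/15 and 5/15.

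Much of this stands. The 70% figure is conditional on the equal-tail version or on letting the exact interval decide. That the power figure came from a 20-patient plan is an inference, supported by the 89.3%, the 6/20 example and the table header, but stated nowhere.

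It does not remove the problem. Section 7.1 judges the sample size by whether the exact interval excludes 5%, and 3/15 fails that check although the 87% version calls it significant. The defence of the power figure therefore conflicts with the sentence that follows it. Pilot status does not help either: 7.1 chose to state a formal test and power, and 3.1 makes a positive study the basis for a larger trial.

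**Conclusion.** The point holds. The precision example is for 20 patients, and the stated power is not reproduced by any two-sided exact test at n=15. At a true rate of 30% the chance of a non-significant result is 29.7% or 12.7%, against the 10% that the plan implies. Only the version with 70% power agrees with the plan's own use of the exact interval. At a true 30%, 17.0% of trials would end at 3/15, where the plan does not settle significance.

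These figures rest on the 5% and 30% rates in 7.1 and on all 15 patients being in the analysis; 7.1 makes no allowance for dropout. This must be fixed, because the only sample-size justification does not describe the trial as planned and the success threshold is undefined.

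**What to change.** Rewrite 7.1 for n=15, naming the two-sided exact test, its critical count and its power.

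- **To agree with the exact interval:** Equal-tail exact binomial test; the 5% null rate is rejected with 4 or more of 15 successes (exact 95% CI for 4/15, 7.8% to 55.1%); power is 70% at a true rate of 30% and reaches 90% at about 39%.
- **If the sponsor prefers the minimum-likelihood test:** state 3 or more of 15, power 87% at 30% and 90% at about 32%, and say openly that the exact interval for 3/15 (4.3% to 48.1%) includes 5%.

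Replace the 6/20 example with 4/15 (7.8% to 55.1%) and 5/15 (11.8% to 61.6%), and change the Table 1 header to n=15. Repeat the chosen test in 7.2 as the primary analysis.

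Separately, state that the 30% bar means 5 or more of 15, that it is reached 48% of the time at a true 30%, and whether it is a decision rule distinct from the test. Whether to align the two is the sponsor's choice.

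The cost is a rewording and a less favourable power figure. No patients or procedures are added.

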7.2 Statistical Methods

Univariate descriptive statistics and frequency distributions will be calculated, as appropriate, for all variables. Baseline values for demographic, clinical, and outcome variables (primary and secondary) will be tabulated. These analyses will help identify potential confounding variables to be used as covariates in advanced statistical (e.g. multivariate) analyses. Bonferroni correction will be used to adjust p-values in the case of multiple comparisons.

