3.3 Secondary Study Endpoints

Secondary efficacy endpoints will include change in: 1) serum AST, total bilirubin, albumin, C-reactive protein, and Mayo PSC risk score⁴² following 12 weeks of curcumin treatment compared to baseline values as markers of biochemical improvement and 2) change in self-reported health status, fatigue severity, and pruritus (as assessed by standardized questionnaires) following 12 weeks of treatment compared to baseline values as markers of symptomatic improvement.

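### For the secondary endpoints, Holm's method would hold the same familywise error as the planned Bonferroni correction and never reject less

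*Combined protocol and SAP*

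**What the plan says.** Section 7.2 states: "Bonferroni correction will be used to adjust p-values in the case of multiple comparisons". It does not list the comparisons, count them, or give a testing order.

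The secondary endpoints come from two places:

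- Section 3.3 lists five biochemical measures: "serum AST, total bilirubin, albumin, C-reactive protein, and Mayo PSC risk score". It adds three symptom domains: health status, fatigue and pruritus.
- Section 3.1 names the instruments. Health status has two ("SF-36 Health Survey and Chronic Liver Disease Questionnaires"); fatigue and pruritus have one each.

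That makes 5 + 4 = 9 secondary comparisons, or 8 if health status is counted once.

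The primary is planned separately. Section 7.1 describes a single exact binomial test at a "nominal two-sided significance level of $\alpha=0.05$ will have approximately 90% power to detect a 25% difference". It gives no power for any secondary endpoint.

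**The concern.** Bonferroni holds every one of the nine secondary p-values to 0.05/9 = 0.0056, however many of the others have already been rejected. Holm applies that threshold only to the smallest p-value and relaxes it step by step. Both methods bound the familywise error at 0.05 without any assumption about how the endpoints are correlated. With 15 patients, power on the secondaries is scarce, so the single-step rule gives some of it up and gains no error control in return.

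What is at stake is modest: how many real secondary changes the pilot can report as significant after adjustment. A second, smaller matter is clarity. Because 7.2 names no family, a reader has to work out from 7.1 that the primary is not part of one.

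**Working it through.** **Inputs from the documents.** n = 15 (section 7.1: "By enrolling 15 patients with PSC in our study"); nine secondary comparisons (sections 3.1 and 3.3); Bonferroni (section 7.2).

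**Assumed, because the documents give no SDs, effect sizes, correlations or dropout rate.** Standardised change 0.8, with 0.5 and 1.0 as a range; correlation between endpoints 0 to 0.6; one-sample t-tests on change from baseline; all 15 patients evaluable. The plan states no secondary power, so there is no figure of its own to reproduce on this point.

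**Step 1: the two rules.** Order the p-values p(1) ≤ … ≤ p(9). Bonferroni rejects each p ≤ 0.05/9. Holm compares p(j) with 0.05/(9 − j + 1), that is 0.05/9, 0.05/8, …, 0.05/1, and stops at the first failure.

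- *Holm never rejects less.* If r of the p-values are at or below 0.05/9, they are the r smallest. Each meets a Holm threshold of at least 0.05/9, so all r are rejected.
- *Same error bound.* With m0 true null hypotheses, Holm's first false rejection must come no later than step 9 − m0 + 1, where the threshold is at most 0.05/m0. The chance that any of m0 true nulls has a p-value that small is at most m0 × 0.05/m0 = 0.05, whatever the correlation.

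**Step 2: Bonferroni power per endpoint.** The noncentrality is 0.8 × √15 = 3.10 with 14 degrees of freedom. At two-sided 0.05 the critical t is 2.14 and power is 82%. At 0.05/9 the critical t is 3.27 and power is 46%. At 0.05/10 it is 3.33, with power of about 45%.

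**Step 3: Holm power per endpoint** (simulation, 20,000 trials per scenario, standardised change 0.8, correlation 0 to 0.6).

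| Endpoints that truly change | Bonferroni, 9 tests | Holm, 9 tests |
|---|---|---|
| 3 | 46-47% | about 48% |
| 5 | 46-47% | about 51% |
| 9 | 46-47% | about 60% |

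Familywise error with Holm stayed below 0.05 with three and with five true effects, and no Bonferroni rejection was lost.

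**Step 4: range over the effect size** (all nine endpoints changing, correlation 0 and 0.5). At a standardised change of 0.5, Bonferroni gives 14% and Holm 15% to 17.5%. At 1.0, Bonferroni gives 71% and Holm 86% to 90%.

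**Step 5: error over primary and secondaries together.** A separate 0.05 for the primary and 0.05 for the secondaries, without a gate, gives a bound of 0.05 + 0.05 = 0.10. If the tests were all independent, the figure would be 1 − 0.95 × (1 − 0.05/9)^9 = 0.0965. With the primary's exact size the bound is 0.0362 + 0.05 = 0.086 (rejecting at 3/15 or more) or 0.0055 + 0.05 = 0.0555 (rejecting at 4/15 or more). The two cutoffs reflect two ways of forming a two-sided exact p-value: minimum-likelihood and doubled-tail. Section 7.1 does not say which applies.

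**Step 6: with a gate.** If the secondaries are tested only after primary success, the overall bound returns to 0.05. Secondary power is then multiplied by primary power, which at a true 30% is 87.3% (cutoff 3/15) or 70.3% (cutoff 4/15), assuming independence.

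- Three endpoints changing: 48.4% × 87.3% = 42%, or 48.4% × 70.3% = 34%, against 44.6% for Bonferroni over ten tests.
- Nine changing: 60.0% × 87.3% = 52%, or 60.0% × 70.3% = 42%, against 44.7%.

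A gated Holm procedure can therefore have less power than a ten-test Bonferroni.

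**The case against.** The best case for leaving the text alone is that Bonferroni is valid, simple and conservative, and that this is a 15-patient open-label pilot. The size of the gain rests on effect sizes that nobody has stated. With three true effects it is about two percentage points. The calculations use t-tests, whereas the Study Summary names a rank test for continuous variables. All of this stands, and it limits the weight of the point. It does not touch step 1, which holds for any valid p-values.

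A reader might also infer that the rule in 7.2 reaches the primary test and could overturn a result of 4/15. The documents do not support that:

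- Section 7.1 plans the primary as one test at 0.05, so the natural reading leaves it unadjusted.
- If the primary were put into the family, the outcome for 4/15 would turn on choices the plan does not make. With the minimum-likelihood p-value of 0.00547, nine tests give 0.049 and ten give 0.055. With the doubled-tail value of 0.01093, they give 0.098 and 0.109.
- 4/15 is 26.7%, which already misses the plan's own condition for further study ("if treatment success is achieved in at least 30% of curcumin treated patients"). The lowest count that meets it, 5/15, has p = 0.00061 or 0.00123. Ten times that is 0.006 or 0.012, still significant.

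Nor can a fall in primary power from 70% to 48% be laid at the rule's door. It would need the primary inside the family. It would also be wrong to pair the 70% with p = 0.00547: the 70% belongs to the doubled-tail test, while under the minimum-likelihood method unadjusted power is 87.3%.

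**Conclusion.** The point holds for the secondary family. Replacing Bonferroni with Holm keeps familywise error at 0.05 within the nine secondary comparisons and loses no rejection. Under the stated assumptions it raises power per endpoint from about 46-47% to about 48%, 51% or 60% when three, five or nine endpoints truly change. The direction is certain; the size is conditional on the assumed effect, the t-tests and 15 evaluable patients.

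It would be tempting to add that error control over the whole trial is unchanged. That is not so if the comparison is with a Bonferroni correction over all ten tests: an unadjusted primary and an ungated secondary family are bounded at 0.10 together, not 0.05. Stating that the primary stands alone only makes explicit what 7.1 already plans. Severity is low: no go decision under the 30% criterion is affected.

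**What to change.** In section 7.2:

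1. List the secondary family (five biochemical and four questionnaire comparisons), and replace Bonferroni with Holm's step-down method at a familywise level of 0.05 for that family.
2. As a clarification, state that the primary exact test is a single comparison at two-sided 0.05 and is not adjusted, in line with 7.1.
3. State that familywise error is controlled within the secondary family and not across primary and secondaries together, where the bound is 0.10. If the sponsor wants 0.05 overall, gate the secondaries on the primary and accept that a power gain over a ten-test Bonferroni is then not assured.

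The cost is three sentences, best written before any outcome data are analysed. No extra patients, visits or measurements are needed. Section 7.2 promises adjusted p-values, which Holm also provides.
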